**Repeat similar table for 10.1.2.2.4.3 Change in NRS 11 Symptoms Score after week 4 and week 8 (by Age Group)**  
**Repeat similar table for 10.1.2.2.4.4 Change in NRS 11 Symptoms Score after week 4 and week 8 (by Geographical Region)**

**Table 10.1.2.2.5.1: Responder Analysis of Satisfactory Relief Assessed by LDQ and/or NRS 11**

FULL ANALYSIS SUBJECT SAMPLE

	Statistics	
 (N=xxx)	
 (N=xxx)
LDQ			
Number of subjects satisfactory relief assessed as:			
Responders	n (%)	xx.x (x.x)	xx.x (x.x)
Non-responders	n (%)	xx.x (x.x)	xx.x (x.x)
	p-value	x.xxx	
NRS 11			
Bloating Sensation			
Number of subjects satisfactory relief assessed as:			
Responders	n (%)	xx.x (x.x)	xx.x (x.x)
Non-responders	n (%)	xx.x (x.x)	xx.x (x.x)
	p-value	x.xxx	
Early Satiety			
Number of subjects satisfactory relief assessed as:			
Responders	n (%)	xx.x (x.x)	xx.x (x.x)
Non-responders	n (%)	xx.x (x.x)	xx.x (x.x)
	p-value	x.xxx	

-----  
Note 1: P-value is calculated by using chi-square test/Fisher Exact test.

Note 2:

**By LDQ Score:**

The subject is considered to be as responder if, at the end of the treatment the overall LDQ score is <9.

**By NRS-11 Score:**

The subject is considered to be as responder if, each NRS11 symptoms change from baseline score at the end of the study treatment is at least 2 (i.e., NRS-11 symptoms CFB  $\geq 2$ ). only subjects with a score of the respective symptom of at least 5 at baseline will be used.

Source: LXX00X.sas, <CRO>.Run DDMMYYYY HH:MM  
Abbott Protocol CCCC-xxx-yyyy

Page x/y

**Table 10.1.2.2.5.2: Responder Analysis of Satisfactory Relief Assessed by LDQ and/or NRS 11 (by Gender)**

FULL ANALYSIS SUBJECT SAMPLE

Group, Characteristics	Statistics	
 (N=xxx)	
 (N=xxx)
Male,	n	xxx	xxx
LDQ			
Number of subjects satisfactory relief assessed as:			
Responders	n (%)	xx.x (x.x)	xx.x (x.x)
Non-responders	n (%)	xx.x (x.x)	xx.x (x.x)
	p-value	x.xxx	
NRS 11			
Bloating Sensation			
Number of subjects satisfactory relief assessed as:			
Responders	n (%)	xx.x (x.x)	xx.x (x.x)
Non-responders	n (%)	xx.x (x.x)	xx.x (x.x)
	p-value	x.xxx	
Early Satiety			
Number of subjects satisfactory relief assessed as:			
Responders	n (%)	xx.x (x.x)	xx.x (x.x)
Non-responders	n (%)	xx.x (x.x)	xx.x (x.x)
	p-value	x.xxx	

-----

---

Note 1: P-value is calculated by using chi-square test/Fisher Exact test.

Note 2:

**By LDQ Score:**

The subject is considered to be as responder if, at the end of the treatment the overall LDQ score is  $< 9$ .

**By NRS-11 Score:**

The subject is considered to be as responder if, each NRS11 symptoms change from baseline score at the end of the study treatment is at least 2 (i.e., NRS-11 symptoms CFB  $\geq -2$ ). only subjects with a score of the respective symptom of at least 5 at baseline will be used.

Source: LXX00X.sas, <CRO>.Run DDMMMYYYY HH:MM  
Abbott Protocol CCCC-xxx-yyyy

Page x/y

*Repeat similar table for* **10.1.2.2.5.3 Responder Analysis of Satisfactory Relief Assessed by LDQ and/or NRS 11 (by Age Group)**

*Repeat similar table for* **10.1.2.2.5.4 Responder Analysis of Satisfactory Relief Assessed by LDQ and/or NRS 11 (by Geographical Region)**

**Table 10.1.2.3.1.1: Treatment Acceptance & Ease of Use Assessment**

FULL ANALYSIS SUBJECT SAMPLE

Response	Statistics	
 (N=xxx)	
 (N=xxx)
Missing	n (%)	xx.x (x.x)	xx.x (x.x)
1-Not all satisfied	n (%)	xx.x (x.x)	xx.x (x.x)
2-Slightly satisfied	n (%)	xx.x (x.x)	xx.x (x.x)
3-Neutral	n (%)	xx.x (x.x)	xx.x (x.x)
4-Very satisfied	n (%)	xx.x (x.x)	xx.x (x.x)
5-Extremely Satisfied	n (%)	xx.x (x.x)	xx.x (x.x)
Treatment Acceptance	n	xxx	xxx
	Mean (SD)	xx.x (x.x)	xx.x (x.x)
	Median	xx.x	xx.x
	Min/Max	xx/xx	xx/xx
p-value		x.xxx	

Note 1: Percentages are based on the number of subjects allocated to treatment.

Note 2: P-value is calculated by using two sample t-test or Mann Whitney U test..

Source: LXX00X.sas, <CRO>.Run DDMMYYYY HH:MM  
Abbott Protocol CCCC-xxx-yyyy

Page x/y

**Table 10.1.2.3.1.2: Treatment Acceptance & Ease of Use Assessment (by Gender)**

FULL ANALYSIS SUBJECT SAMPLE

Group, Response	Statistics	
 (N=xxx)	
 (N=xxx)
Male,			
Missing	n (%)	xx.x (x.x)	xx.x (x.x)
1-Not all satisfied	n (%)	xx.x (x.x)	xx.x (x.x)
2-Slightly satisfied	n (%)	xx.x (x.x)	xx.x (x.x)
3-Neutral	n (%)	xx.x (x.x)	xx.x (x.x)
4-Very satisfied	n (%)	xx.x (x.x)	xx.x (x.x)
5-Extremely Satisfied	n (%)	xx.x (x.x)	xx.x (x.x)
Treatment Acceptance	n	xxx	xxx
	Mean (SD)	xx.x (x.x)	xx.x (x.x)
	Median	xx.x	xx.x
	Min/Max	xx/xx	xx/xx
	p-value	x.xxx	
Female,			
Missing	n (%)	xx.x (x.x)	xx.x (x.x)
1-Not all satisfied	n (%)	xx.x (x.x)	xx.x (x.x)
2-Slightly satisfied	n (%)	xx.x (x.x)	xx.x (x.x)
3-Neutral	n (%)	xx.x (x.x)	xx.x (x.x)
4-Very satisfied	n (%)	xx.x (x.x)	xx.x (x.x)
5-Extremely Satisfied	n (%)	xx.x (x.x)	xx.x (x.x)

Treatment Acceptance	n	xxx	xxx
	Mean (SD)	xx.x (x.x)	xx.x (x.x)
	Median	xx.x	xx.x
	Min/Max	xx/xx	xx/xx
	p-value	x.xxx	

Note 1: Percentages are based on the number of subjects allocated to treatment.

Note 2: P-value is calculated by using two sample t-test/ Wilcoxon signed rank test.

Source: LXX00X.sas, <CRO>.Run DDMMYYYY HH:MM  
Abbott Protocol CCCC-xxx-yyyy

Page x/y

*Repeat similar table for **Table 10.1.2.3.1.3: Treatment Acceptance & Ease of Use Assessment (by Age Group)***

*Repeat similar table for **Table 10.1.2.3.1.4: Treatment Acceptance & Ease of Use Assessment (by Geographical Region)***

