## Exploratory analysis

### ▪ Treatment acceptance and ease of use assessed by using 5-point Likert Scale

The subject's response of treatment acceptance for each point i.e. 1-Not at all satisfied, 2-Slightly satisfied, 3-Neutral, 4-Very satisfied, 5-Extremely satisfied will be summarized descriptively, using frequency count (n) and percentages (%) by Test group and Active Control group at the end of the study treatment (i.e., at week 8).

A descriptive summary of treatment acceptance will also be provided using number of non-missing observation (n), median, minimum (Min) and maximum (Max) by Test group and Active Control.

To find the significant difference of acceptance and ease of use between Test group and Active Control group a two-sample t-test or Mann Whitney test will be used at 5% level of significance based the normality of the data.

Normality of the response of 5-point likert scale scores will be checked by using Q-Q Plot or KS test.

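### The subgroup treatment-acceptance shells name a paired test for two independent arms, and the acceptance shells divide by allocated subjects although they are Full Analysis tables

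*SAP*

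**What the plan says.** The item asks whether the subject is satisfied with the dosing schedule and has five ordered answers (Protocol 8.1). It is collected at visit 4 only (Protocol 8.6, Table 2).

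**Test**
- The Exploratory analysis text after SAP 4.2.2 says that "a two-sample t-test or Mann Whitney test will be used at 5% level of significance based the normality of the data". It adds: "Normality of the response of 5-point likert scale scores will be checked by using Q-Q Plot or KS test". It gives no cut-off and does not say which check governs.
- Note 2 of the overall shell, Table 10.1.2.3.1.1, agrees with that text: "P-value is calculated by using two sample t-test or Mann Whitney U test".
- Note 2 of the by-gender shell, Table 10.1.2.3.1.2, does not: "P-value is calculated by using two sample t-test/ Wilcoxon signed rank test". The remark beneath it has the age-group and region tables (10.1.2.3.1.3 and 10.1.2.3.1.4) repeat this shell.
- SAP 4.7 lists treatment acceptance among the endpoints to be analysed in subgroups by the analysis already specified.

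**Denominator**
- Both shells, and their entries in the table list in SAP 9.3.1, are headed Full Analysis Subject Sample.
- Note 1 in both shells reads: "Percentages are based on the number of subjects allocated to treatment".

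**The concern.** The Wilcoxon signed rank test works on within-pair differences. In a parallel-group trial with one post-treatment answer per subject there is no pair, so it cannot compare the arms. A programmer who follows the shell either cannot run the test or has to invent a pairing, and the printed p-value then depends on that invention.

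The denominator is a separate slip. Allocated to treatment is a defined sample in SAP 4.1, and the Full Analysis sample is a subset of it: subjects must also have been dosed and have at least one post-baseline efficacy assessment. Counting Full Analysis subjects over an allocated base mixes two samples in one percentage.

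What is at stake is the validity of the p-values in three subgroup tables and the percentages in all four acceptance tables.

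**Working it through.** The plan states no figure to reproduce on this point. The check sets the passages side by side and adds illustrations on stated assumptions.

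**1. Which test the SAP intends.** The Exploratory analysis text and the overall shell both offer a t-test or Mann-Whitney. SAP 4.7 carries the specified analyses into subgroups. Its closing phrase mentions only primary, secondary and safety analyses, but treatment acceptance is in the list it governs. Only the by-gender Note 2 names signed rank, so a slip for Wilcoxon rank-sum is the likely explanation.

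**2. What following Note 2 would do.** This used simulated five-point answers.
- With unequal independent arms (140 and 150), the paired test could not be computed.
- With 140 per arm, one data set was drawn from assumed distributions (.03, .07, .15, .40, .35) and (.05, .10, .20, .38, .27). Over 1,000 arbitrary pairings the signed rank p-value ran from 0.0003 to 0.0060. Mann-Whitney gave a single value, 0.0098. All are below 0.05 in this example, but only one of the two tests has a defined answer.

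**3. Denominator.** The inputs are 282 allocated per arm (SAP 3.1) and an assumed Full Analysis count of 253 to 282. The lower end borrows the 253 per arm that the sample-size section requires before drop-out. The category percentage is count / base. The sum of rows is Full Analysis count / 282, if every row, including Missing, counts Full Analysis subjects only.

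| Full Analysis n | 100 answers, allocated base | 100 answers, Full Analysis base | Sum of rows, allocated base |
|---|---|---|---|
| 282 | 100/282 = 35.5% | 100/282 = 35.5% | 282/282 = 100% |
| 268 | 35.5% | 100/268 = 37.3% | 268/282 = 95.0% |
| 253 | 35.5% | 100/253 = 39.5% | 253/282 = 89.7% |

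In the gender shell, Note 1 also leaves open whether the base is the stratum or the whole arm. On a whole-arm base, a stratum of 141 (half the arm, assumed) would have rows summing to 141/282 = 50%.

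Elsewhere the SAP does otherwise. The Full Analysis symptom table for the SF-NDI (Table 10.1.2.2.1.1) uses the Full Analysis count, and the default in SAP 4.2 is subjects with non-missing data. Neither is the allocated count.

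**4. The normality check (secondary).** Five ordered categories cannot follow a normal distribution. In 400 simulated samples per setting, with skewed, symmetric and flat answer patterns, a KS test rejected normality every time at 253 and at 282 per arm. At 25 per group the result depended on the version used. KS with estimated mean and SD rejected in 2% to 49.5% of samples, and the Lilliefors form in 82% to 100%. The check therefore tells us nothing in the overall table and is unstable in small subgroups.

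The effect of the choice between tests was also simulated, with 2,000 trials of 270 per arm. The t-test and Mann-Whitney disagreed at 5% in:
- 4.9% of trials for (.03, .10, .22, .40, .25) against (.05, .14, .26, .36, .19);
- 1.4% with no difference between arms;
- 0% with a larger difference, (.02, .05, .13, .40, .40) against (.05, .14, .26, .36, .19).

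**The case against.** The strongest reply is that the SAP already settles the test. Its text and the overall shell name Mann-Whitney and SAP 4.7 extends the main analysis to subgroups, so the footnote is a single slip inherited by two further tables. With unequal arms the signed rank test would simply fail to run, and the slip would probably be caught. This stands as to intent and likelihood of harm. It does not remove the contradiction in the shell that three tables would be programmed from.

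On the denominator, the default in SAP 4.2 can be overridden by a table's own footnote. That is fair, so the point rests on the mismatch with the table's own heading. The shortfall also disappears if the Full Analysis and allocated counts coincide. The rows would sum to 100% too if Missing counted every allocated subject without an answer, but then the table would no longer be a Full Analysis table.

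On the normality check, a KS test at full sample always leads to Mann-Whitney, so little changes on that route. With no difference between arms, each test rejected in about 4.7% to 4.9% of simulated trials, so neither inflated type I error there. What remains is that "will be checked by using Q-Q Plot or KS test" gives no rule for choosing, least of all in small subgroups.

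A reader might infer three stronger things that the documents do not support:
- That preference for the simpler schedule is the reason for the open-label design. Protocol 4.2 gives the comparison of one tablet with three, which allows both the benefit of fewer tablets and preference to be studied. The item itself asks about satisfaction with the schedule.
- That the percentages are understated as a fact. This depends on a Full Analysis count the documents do not give.
- That the choice of test would often change the result. The 4.9% comes from one scenario with roughly 74% to 75% power, where borderline p-values are common.

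**Conclusion.** The point holds as two footnote errors and one secondary tidy-up. As written, Note 2 of the by-gender shell gives an undefined or arbitrary between-arm p-value in three subgroup tables, although the rest of the SAP shows that Mann-Whitney was meant. Note 1 puts Full Analysis counts over an allocated base. Whenever the Full Analysis sample is smaller than the allocated sample, the percentages are too low and the rows, counting Full Analysis subjects only, do not reach 100%. On the assumed range of 253 to 282 per arm, the shortfall is at most 39.5% − 35.5% = 4.0 percentage points for a category of 100 subjects. The answer distributions and subgroup sizes in the simulations are also assumptions.

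The consequence is small. Acceptance is exploratory in Protocol 3.3, SAP 3.3 and the SAP analysis text. The protocol synopsis does list it as a secondary endpoint, but the protocol plans only descriptive statistics for it and attaches no decision to its p-value. The primary non-inferiority conclusion is unaffected.

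**What to change.** 1. In Note 2 of Table 10.1.2.3.1.2, and so in 10.1.2.3.1.3 and 10.1.2.3.1.4, replace signed rank with Wilcoxon rank-sum (Mann-Whitney).
2. In Note 1 of Tables 10.1.2.3.1.1 and 10.1.2.3.1.2, and the tables that repeat the latter, base percentages on the Full Analysis sample, using the stratum's Full Analysis count by arm in subgroup tables. The whole Full Analysis count keeps the shell's Missing row as a percentage and matches the SF-NDI symptom table. If the non-missing default of SAP 4.2 is preferred, show Missing as a count only and say so.
3. Secondary: in the Exploratory analysis text and Note 2 of all four tables, name Mann-Whitney as the only test and delete the normality check.

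The cost is SAP wording and shell footnotes, to be settled before database lock. Sample size, alpha and data collection do not change.

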**Table 10.1.3.1.1.1: Overall Summary of Adverse Events (by Gender)**  
SAFETY SUBJECT SAMPLE

Group, Characteristics	Statistic	
 (N=xxx)	
 (N=xxx)
Male,	n	xx	xx
Number of Deaths	n (%) E	xx (xx.x%) xx	xx (xx.x%) xx
Number of TE Deaths	n (%) E	xx (xx.x%) xx	xx (xx.x%) xx
Number of Subjects With at Least One SAE	n (%) E	xx (xx.x%) xx	xx (xx.x%) xx
Number of Subjects With at Least One TESAE	n( %) E	xx (xx.x%) xx	xx (xx.x%) xx
Number of Subjects With at Least One TEAE Leading to Study Termination	n (%) E	xx (xx.x%) xx	xx (xx.x%) xx
Number of Subjects With at Least One TEAE	n (%) E	xx (xx.x%) xx	xx (xx.x%) xx
Number of Subjects With at Least One Severe TEAE	n (%) E	xx (xx.x%) xx	xx (xx.x%) xx
Number of Subjects With at Least One TEAE with a Reasonable Possibility for a Causal Relationship	n (%) E	xx( xx.x%) xx	xx( xx.x%) xx
Number of Subjects Without Any TEAE	n (%)	xx (xx.x%)	xx (xx.x%)

Note: n = Number of subjects; E = Number of events.

Note: Percentages are based on the number of subjects in the Safety Subject Sample.

Note: A treatment-emergent adverse event (TEAE) is defined as an AE that started or worsened in severity on or after the first study drug administration and within <xx> days of last study drug administration.

Note: TEAEs leading to study termination are TEAEs reported on the Adverse Event CRF with “Led to Study Termination” = ‘yes’.

Note: Severe = severity reported as “severe” or missing.

Note: Reasonable possibility for a causal relationship = drug-event relationship reported as “possible”, “probable”, “certain” or missing.

Note: [TE] Death is defined as a fatal outcome of a [TE](S)AE.

Source: AET001.sas, <CRO>.Run DDMMYYYY HH:MM  
Abbott Protocol CCCC-xxx-yyyy

Page x/y

*Repeat similar table for **Table 10.1.3.1.1.2: Overall Summary of Adverse Events (by Age Group)***

*Repeat similar table for **Table 10.1.3.1.1.3: Overall Summary of Adverse Events (by Geographical Region)***

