### Default Frequency Tabulations

For qualitative variables, per category the numbers and frequencies of subjects with non-missing data (n, %) will be the default summary presentation, and if appropriate and present, the number of missing values.

For AEs, medical history and concomitant medications, however, the denominator for the percentage calculation will be the number of subjects at risk for the particular treatment arm. A subject will be considered at risk if the subject is in the safety sample and entered the respective study period.

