#### **4.7 Subgroup Analysis**

Primary, secondary efficacy endpoints (LDQ at 4 and 8 weeks, NRS11 (different symptoms), responder rate, functional dyspepsia score by SF-NDI, raw and transformed scores by SF NDI), exploratory endpoint of treatment acceptance and safety endpoints (overall summary of AEs, prolactin levels and change from baseline in prolactin) will be analyzed across subgroups using the same analysis as specified for the primary, secondary and safety endpoints.

The subgroups are defined as follows:

Gender:

- Female
- Male

Age Group:

- $\geq 18$  to  $\leq 44$
- $\geq 45$  to  $\leq 59$
- $\geq 60$

Geographical region (Country):

- Armenia
- Malaysia
- Philippines
- Thailand
- Vietnam

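### The note under the subgroup adverse event tables names the whole safety sample as the denominator; programmed as written, it would scale every subgroup percentage by the subgroup's share of the arm

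*SAP*

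**What the plan says.** SAP section 10.1 gives a shell titled "Overall Summary of Adverse Events (by Gender", and closes it with instructions to repeat the layout for age group and for geographical region. Each gender block opens with that gender's count in each arm, followed by rows of counts and percentages. The footnote reads "Note: Percentages are based on the number of subjects in the Safety Subject Sample", and the program line is "Source: AET001.sas".

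Two other places bear on the denominator:

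- Protocol section 10.1, under Default Frequency Tabulations, says that for adverse events "the denominator for the percentage calculation will be the number of subjects at risk for the particular treatment arm". It then defines the term: "A subject will be considered at risk if the subject is in the safety sample and entered the respective study period". It gives no rule for subgroups.
- SAP section 4.7 lists the overall adverse event summary among the endpoints that "will be analyzed across subgroups using the same analysis as specified for the primary, secondary and safety endpoints". It does not mention denominators.

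The table list in SAP section 9.3.1 shows the three subgroup adverse event tables with a blank output code, which the list defines as non-standard output. SAP section 2 assigns non-standard reporting to Module 1, the document in hand. The shell is therefore the specification that a programmer would follow.

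**The concern.** A row in the male block counts males only. If the percentage beside it is taken over the arm's whole safety sample, the denominator includes women, who cannot contribute to that row. The printed figure then mixes two things, the risk in the subgroup and the size of the subgroup. Subgroups of different size would show different percentages at the same risk.

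The overall summary is the only adverse event output that SAP section 4.7 plans by subgroup. These tables are thus where a reader would look for a difference in tolerability by sex, age or country. The five countries may well enrol unequal numbers, so the effect could be largest there.

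**Working it through.** The documents give no figure for these percentages, so there is nothing to reproduce. The check works out what the footnote would do.

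**Inputs**

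- Arm size: 282, from Protocol section 10.7. It stands in for the number in the arm's safety sample, which is not known in advance.
- Risk of at least one treatment-emergent event: 20% in every subgroup. This is an assumption; 10% and 30% were also tried.
- Subgroup shares of the arm: 10% to 65%. These are assumptions; the documents give no expected split by gender, age or country.
- The footnote is read per arm, in line with the protocol default and the column headings.

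**Formula**

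Let x be the subjects with an event in the subgroup, n the subgroup size in the arm, and N the arm size.

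printed percentage = x/N = (x/n) × (n/N) = true percentage × subgroup share

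**Results at a 20% risk, N = 282** (counts rounded to whole subjects)

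| Share | n | x | x/n | x/N |
|---|---|---|---|---|
| 65% | 183 | 37 | 20.2% | 13.1% |
| 50% | 141 | 28 | 19.9% | 9.9% |
| 35% | 99 | 20 | 20.2% | 7.1% |
| 20% | 56 | 11 | 19.6% | 3.9% |
| 10% | 28 | 6 | 21.4% | 2.1% |

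The 65% and 35% rows together make one arm (183 + 99 = 282). Equal risk in the two genders prints as 13.1% and 7.1%. The 20% row corresponds to five countries of equal size. At risks of 10% and 30%, the 35% share prints as 3.5% (10/282) and 10.6% (30/282).

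**Internal check on the shell**

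The rows for subjects with at least one treatment-emergent event and for subjects without any are complementary, so they should add up to 100% within a gender. For the gender with 99 subjects, 20 with and 79 without give 7.1% + 28.0% = 35.1%, which is simply 99/282.

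**Effect on the comparison of arms within a subgroup**

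At the same 20% risk in both arms, shares of 33% and 37% print as 6.6% and 7.4%, and shares of 30% and 40% print as 6.0% and 8.0%. For an assumed share of 40%, the standard deviation of the chance difference in share between arms is √(2 × 0.4 × 0.6 / 282) = 4.1 points. A typical imbalance of that size moves the printed difference by 0.20 × 4.1 = 0.8 percentage points.

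**Where the footnote seems to come from**

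The program named under the shell carries the code that SAP section 9.3.1 gives to the overall, non-subgroup summary. The shell's number, 10.1.3.1.1.1, is also that of the overall table; the list numbers the by-gender table 10.1.3.1.1.2. The treatment acceptance shells show the same pattern. The by-gender version (Table 10.1.2.3.1.2) repeats Note 1 of the overall version (Table 10.1.2.3.1.1) unchanged, basing percentages on all allocated subjects, and has no subgroup count at the head of its blocks.

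**The case against.** The best case for the plan is that the footnote names the analysis set and nothing more. The gender's own count stands at the head of the block, above the percentage rows, which is the natural place for a denominator. SAP section 4.7 can fairly be read as repeating the analysis within each subgroup, which would restrict the safety sample to that subgroup. The protocol's arm-level default is a general rule and does not address subgroup tables. SAP section 4.3 also refers to Module 2 for the detailed strategy on adverse events, and Module 2 is not among the documents.

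Much of this stands. The shell does not settle which denominator the program would use, and the footnote looks copied, not chosen. A reader might infer that the tables are certain to divide by the whole arm; the documents do not support that. What remains is that the only sentence in the shell stating a basis for the percentages names the wrong group for a subgroup row, and no text supplied replaces it. Module 2 is described as covering standard data, while these tables are listed as non-standard.

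A reader might also infer that subgroups could not be compared at all, or that a small country would always look safe. Neither follows. Counts and subgroup sizes are both printed, so each rate can be recovered by division, and the order of the printed percentages depends on risk as well as share. Nor should a large false difference between arms be expected: at a 40% share, a ten-point gap such as 35% against 45% is about 2.4 standard deviations (10/4.1) from balance under 1:1 randomisation.

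**Conclusion.** The footnote is wrong for a subgroup table and should be corrected. If it is programmed literally, printed percentages are not comparable between subgroups of different size: they shrink in proportion to the subgroup's share, to about a third of the true rate at a 35% share and about a fifth at a 20% share. The sizes rest on assumed shares and event rates with 282 per arm; the proportionality does not.

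The reach is limited. These are three descriptive safety tables, none marked for headline results in SAP section 9.3.1. The primary analysis and the overall adverse event tables are untouched. Comparisons between arms within a subgroup are only slightly distorted unless the shares differ. A literal error could also be noticed, because the complementary rows would not reach 100%.

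**What to change.** In the by-gender adverse event shell and its age-group and region repeats, reword the note to: *Percentages are based on the number of subjects in the respective subgroup and treatment group of the Safety Subject Sample.* At the same time, check Note 1 of the by-gender treatment acceptance shell (Table 10.1.2.3.1.2) and its repeats, where the basis has been carried over in the same way. No separate exception in SAP section 4.7 is needed.

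The cost is one sentence in a shell, plus the check of the second. No data collection, sample size or analysis model changes.
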